Overview: We will enroll adult subjects undergoing clinical echocardiograms at the UCSF Parnassus campus. These subjects will be grouped into derivation and validation cohorts sequentially, stratified by case status, so as to reach the expected sample size. Such grouping will occur after subject enrollment and data collection.

Target Population: Adults with either moderate-to-severe to severe AS or moderate-to-severe to severe MR (cases) and adults with structurally normal hearts with minimal VHD (controls). In a more-stringent, parallel analysis, a target population of controls will be defined as having any degree of AS or MR less than moderate-to-severe.

Accessible Population: Adults meeting the entry criteria undergoing clinical echocardiograms at the UCSF echocardiography laboratory amenable to participation.

Inclusion Criteria:

- Adults > 18 years of age
- Able to provide consent
- Undergoing complete (i.e. not limited) echocardiogram studies

Exclusion Criteria:

- Refusal to participate

Sampling Scheme: We will approach subjects presenting to the adult echocardiography laboratory at UCSF Parnassus consecutively. Additionally, we will pre-screen subjects for a high likelihood of having AS or MR (based on indication for study and prior diagnoses in the APEX medical record) and selectively their enrollment during situations where the enrollment capacity of the study coordinator is saturated.

Recruitment Strategy: Introduction of study at time of registering for echocardiogram with a brochure or flyer, followed by in-person approaching of potential subjects while awaiting the clinical echocardiogram.

Retention Strategy: None. We will retain a master file of the medical record numbers to identify contact information in the future if deemed necessary.

Measurements

Overview: Our study will focus on two measurements: 1) the gold standard assessment of VHD by echocardiogram, as reported by the UCSF echocardiography laboratory. 2) 10 second simultaneous PCG and single-lead ECG recordings by the Eko Duo device at each of the four standard cardiac auscultatory positions. Our study takes advantage of the fact that all clinical echocardiogram reports include these valvular assessments.

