Primary Outcome: Our primary outcome will be the identification of either clinically important MR or AS (either present or absent) by the algorithm on the device measurements from subjects in the validation set. For the primary outcome, we will define our controls as patients with VHD no greater than mild severity as per the gold standard. As our algorithm will provide a score comparing similarity of the learned characteristics with test (validation set) data, we will plot our results as a receiver operating characteristic (ROC) curve at each score. In addition, we will plan to calculate

the likelihood ratios (both positive and negative) of the test at sensitivity cutoffs of 0.9, 0.95, and 0.99.

Secondary Outcome: Our secondary outcome will be substantially the same as our primary outcome, but in this case, we will define our controls as all subjects with less than moderate-to-severe or greater disease of the valvular condition (MR or AS) in question. This will necessitate the generation of a separate algorithm with the derivation set, which we will perform in parallel.

Confounders and Bias: The derivation and validation of our algorithms will occur remotely, after the clinical echocardiogram has been performed, and therefore with no effect on the outcome of the gold standard. Our test may be influenced by the presence of other conditions causing systolic murmurs (including VHD other than AS or MR, or congenital heart disease). We will include these measures from the echocardiogram report to compare test performance in those with and without these other conditions.

Statistical issues

Null Hypothesis: A machine learning algorithm cannot predict the presence of clinically important AS or MR.

Sample Size Justification:

- Sensitivity of Algorithm: 90%
- Specificity of Algorithm: 90%
- Target Likelihood Ratio (+) of Algorithm [LR(R)]: 9 (derived from $Sn / [1 - Sp]$)
- Minimum Likelihood Ratio (+) of Algorithm [LR(R)]: 5
- Confidence Level = 0.95 (α = 0.05)
- Confidence Interval [LR(R)]: 5.120-15.820
- Sample Size = 110 per group; 330 per cohort (control, AS case, MR case); 660 overall (training and validation cohorts)
- Summary: Assuming the sensitivity and specificity of the machine learning algorithm for detection of clinically important AS or MR are both 0.9, a total sample size of 660 is not expected to go below the threshold likelihood ratio of 5.0 in the 95% confidence interval in either the derivation or validation cohorts.

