- Justification of Critical Assumptions: We assume that our algorithm can produce a sensitivity and specificity of 90% in detecting aortic stenosis or mitral regurgitation compared to hearts with no valvular disease, based upon prior published reports using neural networks, using sample sizes of under 100 cases.¹⁰ Furthermore, we estimate a minimum likelihood ratio of 5 would be necessary for the test to be clinically useful. While this estimate works well for our validation set, the number needed for our derivation set is less clear; the estimates above are a conservative number. We anticipate training the algorithm after enrollment of every 20 cases using a bootstrapping approach; this will provide interim test characteristics and help determine the true number needed for the derivation set. As this is, in part, a pilot study, identification of the true sensitivity and specificity of the test is in itself a valuable result.

Analysis approach: We will generate ROC curves (plotting Sn vs. 1-Sp) for algorithm scores for the validation set. Ultimately we will generate 4 curves: two each for MR and AS, using algorithms generated by our primary (defining controls as having no greater than mild VHD) and secondary (defining controls as not having moderate-to-severe or greater VHD) approaches. Additionally, we anticipate performing exploratory, descriptive analyses of the algorithm itself, by identifying clinical correlates to the characteristics most heavily weighted in detecting AS or MR.

Miscellaneous

Ethical considerations: No major concerns. Data will be securely stored on HIPAA compliant platforms. The study qualifies as minimal risk by UCSF CHR criteria.

Pretest plans: Prior to study recruitment, study staff will collect data on themselves and providers to test the data collection system. During initial subject recruitment, study staff will review the process after each day to discuss roadblocks or concerns.

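### The secondary control group is defined in conflicting ways, and under the Secondary Outcome wording the pooled specificity and LR+ depend on a share of other-valve cases that the recruitment design sets

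*Combined protocol and SAP*

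**What the plan says.** The combined protocol and SAP describes the secondary controls in three places.

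- Measurements, Secondary Outcome: "we will define our controls as all subjects with less than moderate-to-severe or greater disease of the valvular condition (MR or AS) in question". The rule looks at one valve at a time.
- Statistical issues, Analysis approach: "secondary (defining controls as not having moderate-to-severe or greater VHD) approaches". This refers to VHD in general.
- Study subjects, Target Population: "a target population of controls will be defined as having any degree of AS or MR less than moderate-to-severe". This is ambiguous, but reads most naturally as both valves lying below the threshold.

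The primary controls are a separate group: "we will define our controls as patients with VHD no greater than mild severity as per the gold standard".

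The recruitment target is "Sample Size = 110 per group; 330 per cohort (control, AS case, MR case); 660 overall (training and validation cohorts"). Subjects are to be "grouped into derivation and validation cohorts sequentially, stratified by case status, so as to reach the expected sample size", and on top of the consecutive approach "we will pre-screen subjects for a high likelihood of having AS or MR". Likelihood ratios are to be reported at fixed sensitivities of 0.90, 0.95 and 0.99. The one planned comparison by control type (Confounders and Bias) concerns other causes of a systolic murmur, and it names valve lesions apart from AS and MR, and congenital disease.

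**The concern.** Under the Secondary Outcome wording, an MR case whose AS is below the threshold is a negative for the AS curve, and an AS case with lesser MR is a negative for the MR curve. The plan's own Significance section says that both lesions produce systolic murmurs, so these may well be the hardest negatives in the study. How many there are is decided by the equal group targets and the case enrichment. It does not come from how often such patients occur in the laboratory.

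Sensitivity is fixed at each reporting point, so LR+ there varies only with the false-positive rate among controls. If that rate differs between ordinary controls and other-valve cases, the pooled ROC curve, specificity and LR+ change with the mix. The same test could then land on either side of the LR+ of 5 that the plan calls the minimum for clinical usefulness.

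Under the Analysis approach wording these subjects drop out. The primary controls leave them out as well, so none of the four planned curves would then show whether the algorithm can tell AS from MR. The two readings answer different questions, and the plan does not say which is meant.

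**Working it through.** **Inputs from the document.** Sensitivity (Sn) 0.90, specificity (Sp) 0.90, minimum LR+ of 5, 95% confidence, and 110 subjects in each of three groups per cohort (Sample Size Justification). The 90% figures are assumed against hearts without valve disease (Justification of Critical Assumptions). No specificity is given for other-valve cases, and no sample size for the secondary control group.

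**Assumed inputs.** The false-positive rate in other-valve cases, their share in other mixes, and the numbers of subjects with intermediate grades or with both lesions.

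**Step 1. Reproduce the plan's figure.**
LR+ = Sn/(1 − Sp) = 0.90/0.10 = 9.
SE(ln LR+) = √[(1 − Sn)/(n₁Sn) + Sp/(n₀(1 − Sp))] = √[0.10/(110 × 0.90) + 0.90/(110 × 0.10)] = 0.288.
95% CI = 9 × exp(±1.96 × 0.288) = 5.120 to 15.820 (unrounded SE), which matches the plan.

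**Step 2. Share of other-valve cases, f, under the Secondary Outcome wording.**
- Target groups only: 110/(110 + 110) = 50%.
- Adding M subjects with mild-to-moderate or moderate disease: 110/(220 + M) = 40%, 33% or 25% for M = 55, 110 or 220.
- If b of the other valve's 110 cases have both lesions, they leave the controls: (110 − b)/(220 − b) = 47%, 44% or 41% for b = 11, 22 or 33.

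Under the Analysis approach wording, f = 0.

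**Step 3. Effect of the share on LR+.**
Pooled false-positive rate = (1 − f) × 0.10 + f × FP_other, and LR+ = 0.90 divided by that rate.

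With FP_other = 0.30 (assumed), and every other control at 0.10:

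| Share f | Pooled Sp | LR+ |
|---|---|---|
| 5% | 0.890 | 8.18 |
| 10% | 0.880 | 7.50 |
| 20% | 0.860 | 6.43 |
| 25% | 0.850 | 6.00 |
| 33% | 0.833 | 5.40 |
| 50% | 0.800 | 4.50 |

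At 50%, with 110 cases and 220 controls, SE = √[0.10/(110 × 0.90) + 0.80/(220 × 0.20)] = 0.139, and the 95% CI is 3.43 to 5.90.

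**Step 4. Dependence on the assumed rate, at f = 50% (110 cases, 220 controls).**

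| FP_other | Pooled Sp | LR+ (95% CI) |
|---|---|---|
| 0.10 | 0.90 | 9.00 (6.03 to 13.44) |
| 0.20 | 0.85 | 6.00 (4.35 to 8.27) |
| 0.30 | 0.80 | 4.50 (3.43 to 5.90) |
| 0.50 | 0.70 | 3.00 (2.43 to 3.71) |

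LR+ equals 5 when the pooled rate is 0.90/5 = 0.18, so 0.05 + 0.5 × FP_other = 0.18 and FP_other = 0.26. With FP_other = 0.10, LR+ stays 9.00 at any mix.

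**Step 5. The same test reported by stratum (FP_other = 0.30).** Ordinary controls, 110 v 110: LR+ 9.00 (5.12 to 15.82). Other-valve cases, 110 v 110: LR+ 0.90/0.30 = 3.00 (about 2.24 to 4.02). Pooling these into 4.50 hides both results.

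**The case against.** The strongest reply is that the Analysis approach wording excludes other-valve cases, so the share may be zero. That stands as a reading, and the concern about the mix is therefore conditional on the Secondary Outcome wording. It does not settle the plan, because the two sections still disagree.

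A reader might infer that half of the secondary controls will be other-valve cases. The document does not support that. The 50% uses only the three target groups, which were sized for precision at 110 per group. The secondary definition also admits intermediate grades, no cap on controls is stated, and subjects with both lesions leave the pool. At the target numbers, 50% is an upper bound.

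A reader might also infer that the quota, and not the test, determines specificity and LR+. That goes too far. The mix sets only the weights, and the false-positive rates belong to the test. A separate algorithm is to be trained for the secondary definition. Under the Secondary Outcome wording it would learn from other-valve cases as negatives, so their false-positive rate could be low. The document gives no value for it.

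Finally, no success rule is tied to the secondary LR+, and the study calls itself partly a pilot. Both points limit the consequence. Neither supplies a control definition or a breakdown by control type.

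**Conclusion.** The concern holds in a limited form. The secondary control group is defined inconsistently. Under the Secondary Outcome wording, other-valve cases may make up as much as 50% of it, and the pooled results depend on that share whenever the false-positive rate differs between control types. In the illustration LR+ moves from 7.5 at a 10% share to 4.5 at 50%, across the plan's minimum of 5. That crossing rests on the assumed specificity of 0.70 in other-valve cases; at a 50% share it needs a false-positive rate above 0.26 in them. Nothing in the document shows that the rate will be that high, or that the secondary analysis will miss 5. What can be said is that the pooled figure alone would not let a reader tell a weak test from a demanding mix, and that the planned comparison by other murmur-causing conditions does not call for this separation.

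**What to change.** 1. Reconcile Target Population, Secondary Outcome and Analysis approach into one secondary control definition. State explicitly whether a subject with clinically important disease of the other valve is a control.
2. Report the secondary specificity and LR+ separately for mutually exclusive control strata, assigned in this order:
   - (c) clinically important disease of the other valve (dictionary codes 5 to 7), whatever the sub-threshold grade of the valve in question;
   - (b) otherwise, mild-to-moderate or moderate disease (codes 3 and 4);
   - (a) no more than mild disease (codes 0 to 2).

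   If the agreed definition excludes stratum (c) from the controls, it can still be reported as a separate comparison, so that the ability to tell AS from MR is examined.
3. If a pooled figure is given, say that it reflects the enrolled mix. Weighting it to the laboratory's mix is an optional sensitivity analysis. It would need enrolment route to be recorded, since the data dictionary has no such field, or a count of laboratory reports that the plan does not now describe. Whether that mix is the right target is also open to argument.

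Items 1 and 2 need only analysis text, because the AS and MR grades are already abstracted. The downside is smaller strata and wider intervals.

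### The printed LR+ interval assumes a cutoff fixed in advance; if cutoffs are located on the validation ROC, as the plan most naturally reads, the interval is wider and its lower limit falls below 5 unless the curve is steep there

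*Combined protocol and SAP*

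**What the plan says.** In the combined protocol and SAP, under Statistical issues (Sample Size Justification), the algorithm is assumed to have sensitivity and specificity of 90% each, so that LR+ is 9. There are 110 subjects per group. The plan sets "Minimum Likelihood Ratio (+) of Algorithm [LR(R)]: 5" and prints "Confidence Interval [LR(R)]: 5.120-15.820" at the 95% level. The Summary bullet concludes that "a total sample size of 660 is not expected to go below the threshold likelihood ratio of 5.0 in the 95% confidence interval", and applies this to both cohorts.

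The analysis is described elsewhere. Under Primary Outcome, algorithm scores in the validation set are plotted as an ROC curve, and the plan will calculate "the likelihood ratios (both positive and negative) of the test at sensitivity cutoffs of 0.9, 0.95, and 0.99". The Analysis approach paragraph repeats that the ROC curves are drawn from validation-set scores. No section says whether the score cutoffs for those three sensitivities come from the derivation set or from the validation ROC. None names an interval method for the reported LRs.

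**The concern.** The operating points in the Primary Outcome text are sensitivities, not score values. To read LR+ at sensitivity 0.90 on the validation ROC, one finds the score that 90% of the 110 validation cases exceed, then counts the controls above it. That score is an estimate, and its error passes into the false-positive rate. The printed interval has no term for this.

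It matters because this interval is the only precision figure supporting the 660 subjects, and because the plan takes an LR+ of 5 as the least that would be clinically useful. If the same type of interval were later attached to LRs read from the validation ROC, it would be too narrow and would clear 5 too easily.

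**Working it through.** **Inputs from the Sample Size Justification.** Sn = 0.90; Sp = 0.90, so the false-positive rate F = 0.10; n1 = 110 cases of one lesion; n0 = 110 controls; LR+ = 0.90/0.10 = 9; two-sided 95%, z = 1.96; threshold 5.

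**Input not in the documents (assumption).** b = dF/dSn at the operating point. This is the ratio of control to case score density at the cutoff, or the reciprocal of the usual ROC slope. With normal scores and a curve through Sn = Sp = 0.90, b equals the case-to-control SD ratio, so b = 1 means equal variances.

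**Step 1: reproduce the printed figure (cutoff known in advance, two independent binomials).**

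SE² of ln LR+ = (1−Sn)/(n1·Sn) + (1−F)/(n0·F) = 0.1/99 + 0.9/11 = 0.08283, so SE = 0.2878.

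9·exp(±1.96 × 0.2878) = 5.120 to 15.820, an exact match.

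**Step 2: cutoff located on the validation cases at sensitivity 0.90.** The numerator is now fixed at 0.90 and only F varies:

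SE² of ln LR+ = (1−F)/(n0·F) + b²·Sn(1−Sn)/(n1·F²) = 0.08182 + b² × 0.09/(110 × 0.01) = 0.08182 × (1 + b²).

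| b (assumed) | SE | Expected 95% interval |
|---|---|---|
| 1/9 | 0.2878 | 5.12–15.82 |
| 0.3 | 0.2986 | 5.01–16.16 |
| 0.5 | 0.3198 | 4.81–16.84 |
| 0.7 | 0.3492 | 4.54–17.84 |
| 1 | 0.4045 | 4.07–19.89 |
| 1.5 | 0.5157 | 3.28–24.73 |

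A concave ROC through this point must have b between 1/9 and 9. The printed interval is therefore the narrowest case.

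**Step 3: when does the lower limit stay at 5?** This requires SE ≤ ln(9/5)/1.96 = 0.2999, so SE² ≤ 0.08994. Then b² ≤ 0.08994/0.08182 − 1 = 0.0992, and b ≤ 0.315. As a measure of size only: at b = 1, about 201 per group would give a lower limit of 5, against 110 planned.

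**Step 4: coverage if the printed interval type were used with validation-located cutoffs.** Simulation used equal-variance normal scores, 110 v 110, and runs of 20,000 data sets. Coverage of the nominal 95% interval was about 86–88% at sensitivity 0.90, 74–76% at 0.95 and 50% at 0.99. The spread at a given sensitivity is between runs and probably reflects how the empirical cutoff is defined. With a known cutoff the same interval covered 95–96%.

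**The case against.** The strongest reply is that the formula is right for a fixed operating point, and that the documents do not exclude one. The study has a derivation cohort. If score cutoffs are locked there and applied unchanged to the validation cohort, the second term in Step 2 disappears and 5.120–15.820 is the correct expected interval. This stands, and it makes the point conditional on where the cutoffs are set. It does not remove the point, because the plan never says that cutoffs are carried over. Locked cutoffs would also not in general give validation sensitivities of 0.90, 0.95 and 0.99, which is how the Primary Outcome text describes the LRs.

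Second, b is not in the documents, so no single replacement figure is established. This also stands. With a case-to-control SD ratio of 0.5, simulated coverage of the printed interval type at sensitivity 0.90 was 94%, and at 0.3 it was 96%, so under-coverage there is not a feature of every curve.

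Third, the plan names no interval method for the reported LRs, claims precision only at Sn = Sp = 0.90, sets no pass/fail rule on the lower limit, and calls itself in part a pilot. A reader might infer that the reported intervals will be wrong, or that the trial will wrongly declare success. The documents support neither inference; the under-coverage arises only if the printed type of interval is carried into the results with validation-located cutoffs.

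**Conclusion.** The point holds as a mismatch between the precision calculation and the most natural reading of the planned analysis. It is not an arithmetic slip, although a reader might take it for one: Step 1 reproduces the printed limits exactly. A reader might also infer that no LR in the report can have the printed precision, or that the lower limit is certain to be under 5. Neither follows, because cutoffs locked in the derivation set, or b no more than about 0.315 for the lower limit, would be exceptions.

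What the documents do not support is the unconditional statement that 5 is protected. If cutoffs are located on the validation ROC, the expected lower limit at sensitivity 0.90 is 4.81, 4.54, 4.07 or 3.28 for b of 0.5, 0.7, 1 or 1.5. These figures rest on the plan's own Sn, Sp and group sizes, the large-sample variance in Step 2, and an assumed b. The coverage figures rest further on equal-variance normal scores.

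**What to change.** 1. **Sample Size Justification.** Label 5.120–15.820 as applying only to a score cutoff fixed before the validation data are seen. For LR+ at sensitivity 0.90 on the validation ROC, give the range in Step 2 with its assumption on b. Withdraw the unconditional statement about the limit of 5.

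2. **Analysis approach.** State where the cutoffs are set and match the interval to that choice, in one of two ways:
   - Lock the score cutoffs in the derivation set, report the sensitivity and specificity actually obtained in validation, and use the independent-binomial interval.
   - Locate the cutoffs on the validation ROC, and use a bootstrap that resamples cases and controls separately by subject and re-locates the cutoff in every resample. In small simulations (400–500 data sets) this covered 96–97% at sensitivity 0.90 and 95.4% at 0.95.

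3. **Sensitivity 0.99 with validation-located cutoffs.** Report this LR as descriptive only. The cutoff then rests on one or two of 110 cases, and the bootstrap may also under-cover: one simulation of 1,500 data sets gave 83%, and 75% under another cutoff rule. Those figures were not independently repeated and serve as a warning.

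The cost is SAP wording and a few lines of code, with no extra patients. The downside is that the stated precision becomes less favourable.

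### The boundary between derivation and validation is drawn only after interim training has used labelled subjects; fix it, and reserve 110 per group for validation, before the first training

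*Combined protocol and SAP*

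**What the plan says.** Four places in the combined protocol and SAP bear on this.

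- **Study subjects, Overview.** Subjects are assigned to the two cohorts in sequence, stratified by case status, to reach the planned size. On timing: "Such grouping will occur after subject enrollment and data collection".
- **Statistical issues, Sample Size Justification.** Each cohort has 110 controls, 110 AS cases and 110 MR cases, so 330 per cohort and 660 in all. Sensitivity and specificity are both taken as 90%. The threshold is "Minimum Likelihood Ratio (+) of Algorithm [LR(R)]: 5" and the resulting interval is "Confidence Interval [LR(R)]: 5.120-15.820".
- **Statistical issues, Justification of Critical Assumptions.** The size is said to suit validation. The number needed for derivation is described as less certain, and the figure given as conservative. Training is anticipated after each 20 cases "using a bootstrapping approach; this will provide interim test characteristics and help determine the true number needed for the derivation set".
- **Miscellaneous, Data Management Plan.** At training times specified in advance, the machine learning team receives the key linking subject identifiers to valve disease category.

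The primary outcome is defined on the validation set. The plan does not say whose labels are released at each training, when interim training stops, what interim result makes derivation large enough, or whether the 110 per group in validation is held fixed. It does not describe the bootstrap further.

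**The concern.** A validation set supports an unbiased estimate of performance if its membership does not depend on how the algorithm performs and if none of its members helped to train it. The rules above secure neither condition. Training, labels and interim performance all come during enrolment; the assignment that should separate the two cohorts comes afterwards, and one of its inputs, the derivation number, is left open to the interim results.

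Two things are at stake. If a subject used in an interim training were later counted in validation, the algorithm would be scored partly on its own training data, and sensitivity and specificity would tend to come out too high. If the boundary moved so that fewer subjects were left for validation, the stated likelihood ratio interval would no longer describe the study.

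**Working it through.** **1. Order of events.** Set side by side, the sections give this sequence: enrol 20 cases; release labels; train and obtain interim test characteristics; repeat; finish enrolment and data collection; assign cohorts. Assignment in sequence would protect validation if the cut-point were fixed and training never reached beyond it. No section fixes the cut-point or stops training there.

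An illustration of the exposure: planned cases are 2 × (110 + 110) = 440, of which 220 are for derivation. Assume that the 20 cases count AS and MR together, that the two accrue evenly, and that training runs to the end of enrolment; the plan states none of these. There would then be 440/20 = 22 trainings. Only the first 220/20 = 11 could be confined to derivation cases by enrolment order alone.

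**2. The plan's own interval.** Inputs from the Sample Size Justification: Sn = Sp = 0.90, 95% confidence, 110 cases and 110 controls.

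- LR+ = Sn/(1 − Sp) = 0.90/0.10 = 9
- SE(ln LR+) = √[(1 − Sn)/(Sn × cases) + Sp/((1 − Sp) × controls)] = √[0.1/(0.9 × 110) + 0.9/(0.1 × 110)] = √(0.00101 + 0.08182) = 0.2878
- Limits = 9 × exp(±1.96 × 0.2878) = 5.120 and 15.820

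This matches the stated interval to three decimals.

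**3. How far validation can shrink.** For equal groups the lower limit is at least 5 when n ≥ (1/9 + 9)/[ln(9/5)/1.96]² = 101.3, so 102 per group.

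| Cases = controls in validation | Lower 95% limit of LR+ |
|---|---|
| 110 | 5.120 |
| 102 | 5.010 |
| 101 | 4.996 |
| 90 | 4.824 |
| 80 | 4.645 |

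The margin is 110 − 102 = 8 per group for an equal reduction. Controls are the binding group, since they supply 0.08182 of the 0.08283 variance in step 2. With 110 cases, 102 controls are still needed (5.011; 101 gives 4.997). With 110 controls, 14 cases would keep the limit at 5.003.

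**4. Bootstrap scoring (secondary).** A resample of n subjects contains a share 1 − (1 − 1/n)ⁿ of them, which is 0.637 at n = 40. A learner that memorises, has no true signal and is scored on the whole original sample would be right 0.637 + 0.363 × 0.5 = 0.82 of the time. A simulated ridge linear classifier with no signal, also scored on the whole sample, gave 0.68 (10 features) to 0.82 (50 features) at 20 per group, and 0.56 to 0.66 at 110 per group. Scored on left-out subjects it gave about 0.50, the true value. The learners, feature counts and early group size are assumptions; the documents give none of them.

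**The case against.** The natural reading is that interim training uses derivation subjects, that sequential assignment puts early enrollees in derivation, and that 110 per group remains for validation. The plan states 330 per cohort, calls its derivation figure conservative and releases labels only at times specified in advance. All of that is in the text and makes a good outcome likely. What remains is that the plan also puts the assignment after data collection and lets interim results inform the derivation number, so that outcome rests on conduct and not on a rule.

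A reader might infer more than the documents support:

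- **That derivation will grow at validation's expense.** No section says so. Nor is 660 stated as a cap that rules out further enrolment. An optimistic interim result would more naturally end derivation early, which does not shrink validation.
- **That people who have seen interim results draw the boundary.** The plan does not say who draws it.
- **That the interim estimates are inflated.** Scoring on left-out subjects is itself a bootstrap method, so the text is compatible with sound practice. The value 0.82 is the top of an assumed range. Inflation at an interim look would not bias the validation result if validation subjects are kept out of training.

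The 102 threshold is also not a cliff. It concerns the interval expected at exactly Sn = Sp = 0.90. By simulation under that assumption, the observed lower limit reaches 5 in about 57% of studies at 110 per group and about 52% at 102.

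**Conclusion.** The concern holds as a gap between stated rules. Training with labels and interim performance precedes cohort assignment, the derivation number is open to those results, and no rule keeps trained-on subjects out of validation. The documents do not show that contamination or a smaller validation set will occur, and they give no basis for sizing the bias if it did.

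The precision at risk can be sized. At Sn = Sp = 0.90, an equal cut to below 102 per group takes the lower limit under the plan's minimum of 5, and controls drive this. The result rests on the plan's assumed accuracy and on the log method, which reproduces its interval.

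The unspecified bootstrap is a point of wording, not a demonstrated error. With no signal, scoring on the full sample gave about 0.56 to 0.82 against a true 0.50, depending on the assumed learner and sample size.

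**What to change.** 1. Replace the assignment rule in Study subjects, Overview with a boundary set before the first training, for example by enrolment order within each group. Reserve 110 controls, 110 AS cases and 110 MR cases for validation. Give each subject one cohort only, including those with both lesions and those with intermediate grades, who enter only the secondary analysis as controls.
2. In the Data Management Plan, limit label release to derivation subjects until the algorithm is locked.
3. In Justification of Critical Assumptions, state that interim results may shorten derivation or change the algorithm but may not draw on the reserved subjects.
4. If validation is made smaller anyway, restate the likelihood ratio interval for the actual numbers of cases and controls.
5. Wording: state that interim performance is scored on left-out subjects and that whole subjects are resampled, so that one person's four recordings stay together.

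The cost is a few sentences and some flexibility: derivation cannot grow within the 660 at validation's expense. Interim figures may look less favourable than under full-sample scoring. With real signal, left-out scoring can read slightly low (0.65 against a true 0.68 at 20 per group with 10 features, in the assumed simulation).
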